## For percutaneous IR biopsy (sites not collecting fresh frozen samples)

Core Biopsy Number	Processing Details	Purpose
1 - 2	FFPE, once diagnosis is made, ship diagnostic block to NHS GG&C Biorepository (≥ 1cm tumour per core)	Diagnostic purposes, then Genomic analysis (targeted gene panel sequencing), +/- transcriptomic analysis (RNAseq), and IHC analyses if necessary

FFPE = formalin fixed and paraffin embedded; NHS GG&C = NHS Greater Glasgow and Clyde; WGS = whole genome sequencing

#### 4.1.2 Visit 2: Molecular Profile Consent and Screening Assessment (Consent 2)

 Once a diagnosis of pancreatic cancer is established and research tumour biopsies have been obtained, patients must give additional, separate, written informed consent for Precision-Panc Master Protocol molecular phenotyping of their biopsy sample (Consent 2).

Master Protocol; v2; 6th October 2017

- 2. Eligibility assessment: as per Section 3.2.
- 3. The site will then contact CRUK CTU Glasgow to obtain a Master Protocol ID.
- 4. Demographics data, medical, family, and cancer history: medical history is obtained and documented including prior diagnosis, prior treatment and concomitant diseases.
- 5. Whole blood sample for germline and circulating biomarker analysis will be taken (for more details, please refer to Master Protocol lab manual).
- 6. The research biopsies should then be sent to Glasgow Bio-repository for where they will be logged and processed. Some samples will be extracted at the Wolfson Wohl Cancer Research Centre. Analyses of the materials and generation of the molecular profile will also take place at the WWCRC (please see lab manual for full details regarding shipping).

#### 4.2 **Laboratory Tests**

All tissue samples collected will be transported to their local NHS Biorepository in the format as outlined in the Lab manual before transported to NHS GG&C Biorepository and Laboratory Genetics Department where they will be logged and the sample quality reviewed. Please refer to the lab manual for details on the logistics of tissue sample handling, shipping, processing, and the types of molecular analyses to be performed.

#### 4.3 Duration of Trial Participation and Master Protocol Follow-up

Patients recruited on the Master Protocol who have pancreatic cancer, and sufficient tumour material to produce a satisfactory molecular profile, will be followed up until death. In addition to the information collected on eCRF by Glasgow CRUK CTU such as adverse events associated with study specific interventions (biopsy, blood sample), and the annual collection of overall survival and anti-cancer treatment, further information will be accessed via routine NHS IT systems, or a periodic data collection exercise performed by site PIs or his/her delegates to facilitate downstream translational research of Precision-Panc.

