#### 2.2 Secondary Objective(s)

 To assess the overall survival (OS) in patients enrolled in Precision-Panc and relate this to molecular profile information.

Master Protocol; v2; 6th October 2017

- To assess the safety of obtaining tumour biopsies suitable for molecular profiling within a standard patient treatment pathway.
- To establish a central repository of molecular profiles with accompanying phenotypic data and accompanying biospecimens for further translational research.
- To establish a dynamic platform for evaluation of circulating biomarkers to subsequently inform design of subsequent clinical studies.

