#### 3 TRIAL DESIGN

The purpose of the Precision-Panc Master Protocol is to define general eligibility criteria for patient recruitment. Eligible patients will be invited to undergo an additional tumour biopsy (either at the time of their diagnostic biopsy [preferable] or at a repeat biopsy, if agreeable). The samples obtained from this biopsy will be subjected to molecular profiling to deliver a molecular profile report based on the analyses of tumour and blood to enable patient enrolment for Precision-Panc PRIMUS studies.

Each of the PRIMUS studies will contain a unique schedule of assessments and eligibility criteria. Once patients have completed participation on a PRIMUS study, they may have the option (based on their longitudinal molecular profiling and fulfillment of eligibility criteria) to enter another PRIMUS study in the Precision-Panc portfolio. Patients will be followed up as part of the individual PRIMUS studies, or if the patients are not suitable for enrolment to recruiting PRIMUS studies, they will be followed up on the Master Protocol.

Patients with a confirmed diagnosis of pancreatic cancer, in whom sufficient tumour material can be obtained to produce a satisfactory molecular profile, will be followed up on the Master Protocol. In addition to the information collected on eCRF by Glasgow CRUK CTU such as adverse events associated with study specific interventions (biopsy, blood sample), and the annual collection of overall survival and anti-cancer treatment, further information will be accessed via routine NHS IT systems, or a periodic data collection exercise performed by site PIs or his/her delegates to facilitate down-stream translational research of Precision-Panc. This will be explained explicitly on the PIS. In addition to the approvals of the relevant governance committees, access to patient data held within the NHS is subject to the provision of consent of patients to share data regarding their treatment and current disease status. The patient information sheet and consent forms associated with the Master Protocol provide the options for patients to opt out of this longer term follow-up data collection.

The Precision-Panc Master Protocol implements a state-of-art molecular screening mechanism for patients with pancreatic cancer to facilitate clinical trial enrollment. Through this process, a wealth

Master Protocol; v2; 6th October 2017

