#### 3.4 **Registration**

To register a patient on the trial and/or to obtain either a screening number or a Master Protocol ID, contact the CRUK Clinical Trials Unit, Glasgow. Registration to the trial can be performed by either telephone or fax on the following numbers:

[contact] [contact]

The patient's eligibility criteria will be reviewed and confirmation given that the consent for research biopsy (Consent 1) has been obtained before an initial **screening ID** will be allocated.

Once cancer is confirmed and the patient gives consent for Master Protocol molecular profiling (Consent 2) the Glasgow CRUK CTU will be contacted a second time and a Precision-Panc **Master Protocol ID** will be generated

Master Protocol; v2; 6th October 2017

All patients must be screened and registered onto the Master Protocol prior to commencement of any study procedure. With the patient's consent the participant's GP will be informed of their involvement in the trial.

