If the patient withdraws from the Precision-Panc Master Protocol, it should be clearly documented in the patient's notes what they are withdrawing from (consent to use any past data, consent to use any samples collected or consent for further data collection from the date of consent withdrawal). If a patient withdraws their consent from the trial the site must document this is the study electronic Case Report Form (eCRF).

In addition to the scenario where an individual patient may voluntary withdraw from Precision-Panc Master Protocol, the study team may also withdraw patient from Precision-Panc in the rare incidents that sufficient tumour material cannot be obtained to produce a satisfactory molecular Master Protocol; v2; 6th October 2017

profile, even through multiple attempts, especially if further biopsy attempt is deemed harmful. This is explained explicitly in the PIS.

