#### 7 Trial Closure/Definition of end of trial

No patients will be recruited to the Precision-Panc Master Protocol after 5 years unless additional funding and approval is secured and appropriate protocol amendments are in place. Patients registered to the Precision-Panc Master Protocol will continue to be followed up until death via access to routine NHS systems and the study eCRF.

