#### **Consent 2: Master Protocol Molecular Profiling consent**

After tumour biopsy is performed, and a cancer diagnosis is established, patients will be required to give informed consent for molecular profiling to be performed on tumour tissue (with or without germline analysis), and to be enrolled on to Precision-Panc Master Protocol. Peripheral blood will also be drawn at this time to be used as a source of normal genomic DNA for molecular profiling.

Consent for each stage must be sought from each participant only after full explanation has been given, an information sheet offered and adequate time allowed for consideration. Signed participant consent must be obtained, the consent forms should also be signed by the person carrying out the consent procedure at site, who must be detailed on the study specific delegation and training log as having authorisation. The PI is responsible for ensuring if the taking of consent is delegated to a designee, the designee is suitably qualified by training or experience to take informed consent.

The right of the participant to refuse to participate without giving reasons must be respected. All participants are free to withdraw at any time from the protocol treatment without giving reasons and without prejudicing further treatment.

An original completed consent form must be retained at each site in the appropriate section of the Investigator Site File, and a photocopy placed in the patient's medical records. All patients must be given either an original or a copy (as per local site practice) of the signed patient information sheet and consent form for their records. Consent forms must be retained on site and not submitted to the Precision-Panc team. Each site shall confirm to the CRUK Glasgow CTU that consent has been obtained. The CRUK Glasgow Centre in turn shall notify the CI/WWCRC Project Manager of this consent status.

In the event that new patient information sheets/consent forms are produced throughout the duration of the trial, it maybe that patients already participating in the trial should be reconsented to the updated version of the patient information sheet. However, if the principal investigator decides that this is not in the best interests of the patient re-consent is not required. Decisions to not re-consent patients must be documented in the patient's medical records.

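### The protocol contradicts itself on who is followed for survival: all registered patients, or only those with a satisfactory molecular profile

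*Protocol*

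**What the plan says.** **Objective.** Section 2.2: "To assess the overall survival (OS) in patients enrolled in Precision-Panc and relate this to molecular profile information".

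**Enrolment.** Under section 10.2, Consent 2 is where patients agree to profiling and "to be enrolled on to Precision-Panc Master Protocol". Under section 3.4, the Master Protocol ID requires confirmed cancer and Consent 2; a profile is not a condition. In section 4.1.2 the ID is step 3 and the blood sample step 5. Only at step 6 does the tissue move: "The research biopsies should then be sent to Glasgow Bio-repository for where they will be logged and processed".

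**Follow-up with a tissue condition.** Section 4.3 covers patients with pancreatic cancer and "sufficient tumour material to produce a satisfactory molecular profile, will be followed up until death". Section 3 has a paragraph to the same effect.

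**Follow-up without one.** Section 7: "Patients registered to the Precision-Panc Master Protocol will continue to be followed up until death". A separate sentence in section 3 deals with patients who do not fit an open PRIMUS study: "if the patients are not suitable for enrolment to recruiting PRIMUS studies, they will be followed up on the Master Protocol".

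**Withdrawal.** Section 3.5: "the study team may also withdraw patient from Precision-Panc in the rare incidents that sufficient tumour material cannot be obtained". The same section keeps patients in follow-up after they withdraw consent if their profile is complete, unless they also refuse follow-up. It has no matching provision for patients the team withdraws for lack of tissue.

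**The concern.** The protocol defines two follow-up populations that cannot both apply. A site working from section 4.3 may stop at tissue failure; a site working from section 7 would carry on.

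If the narrower definition is applied, whether a patient's death is recorded depends on a laboratory result obtained after enrolment. Adequate tissue may depend on lesion site, biopsy route, repeat attempts and whether a further attempt is judged harmful, and any of these could be related to prognosis. OS in enrolled patients would then become OS in patients with adequate tissue. With no outcomes for the failures, nobody could test whether the two differ.

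A second loss concerns the blood samples. Blood for germline and circulating-biomarker work is taken at Visit 2 before the tissue is processed, and circulating biomarkers appear in both the primary and a secondary objective. Tissue failures would have usable blood data and no survival outcome to set against it.

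**Working it through.** **Step 1: the texts side by side**

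| Section | Who is followed | Tissue condition |
|---|---|---|
| 2.2 (objective) | Enrolled patients | No |
| 3, sentence on PRIMUS suitability | Patients not suitable for an open PRIMUS study | No |
| 3, next paragraph | Confirmed cancer | Yes |
| 4.3 | Confirmed cancer, until death | Yes |
| 7 | Registered patients, until death | No |

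The sequence in section 4.1.2 settles the timing. Biopsies must have been taken before Consent 2, so the first attempt precedes enrolment. Whether the tissue is adequate, and any repeat attempt, comes afterwards. The enrolled population therefore includes later tissue failures, and sections 3 and 4.3 leave them out.

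**Step 2: is there a figure to reproduce?** No. Section 6.1 declines an overall sample size, and no tissue-failure rate is given.

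**Step 3: illustration of possible size**

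Inputs from the protocol: median survival of 6 months and 90% dead within a year (section 1.1); 2,500 to 5,000 patients (section 3.1).

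Assumptions, not in the protocol: failure share f from 2% to 30%; death hazard ratio h from 1 to 2 for failures against profiled patients; the 6-month median applies to all enrolled patients.

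Model: S(t) = (1−f)·exp(−λt^k) + f·exp(−hλt^k), with S(6) = 0.5. Writing x = exp(−λ·6^k), solve (1−f)x + f·x^h = 0.5. The profiled-only median is 6·(ln 2 / −ln x)^(1/k).

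Two shapes were used:
- Exponential: k = 1. This implies 25% alive at one year when h = 1, against 10% in section 1.1.
- Weibull: k = ln(ln 10 / ln 2)/ln 2 = 1.73, which passes through 50% at 6 months and 10% at 12 months.

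Worked case (f = 0.30, h = 2, exponential): 0.3x² + 0.7x − 0.5 = 0, so x = (−0.7 + √1.09)/0.6 = 0.573. Then −ln x = 0.556, and the median is 6 × 0.693/0.556 = 7.48 months.

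Profiled-only median in months, exponential / Weibull, where the all-enrolled median is 6.0:

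| f | h = 1 | h = 1.25 | h = 1.5 | h = 2 |
|---|---|---|---|---|
| 2% | 6.00 / 6.00 | 6.03 / 6.02 | 6.05 / 6.03 | 6.09 / 6.05 |
| 10% | 6.00 / 6.00 | 6.14 / 6.08 | 6.26 / 6.15 | 6.45 / 6.26 |
| 30% | 6.00 / 6.00 | 6.43 / 6.24 | 6.81 / 6.45 | 7.48 / 6.81 |

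Patients outside section 4.3 follow-up would number from 50 (2% of 2,500) to 1,500 (30% of 5,000). Section 3.1 counts patients recruited, consented and screened, so these figures are too high if fewer reach Consent 2.

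**The case against.** **Section 7 already follows everyone.** On its face it does, so it would be wrong to infer that follow-up is simply limited to profiled patients. But section 7 deals with closure, and its verb can be read as continuing whatever follow-up was already under way. Section 4.3 is the operative follow-up section and says something different. The contradiction stands.

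**Tissue failure is described as rare.** Section 3.5 uses that word for withdrawal after several attempts, and the withdrawal is optional. If failures as a whole are that uncommon, the effect on the median is negligible, as the 2% row shows. The condition in sections 3 and 4.3, however, applies to every patient without a satisfactory profile, and no rate is given.

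**Failures remain visible.** A reader might infer that tissue failures vanish from the study and take with them the evidence on whether the screening framework works. The protocol does not support that. They hold a screening ID and a Master Protocol ID, baseline data are collected at Visit 2, and samples are logged and quality-checked (section 4.2). No text deletes the data of a patient the team withdraws. They can be counted; only their later survival is at risk.

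**PRIMUS participation.** A reader might also infer that patients who suit a PRIMUS study but decline it are followed nowhere. For those with adequate tissue, the next paragraph of section 3 and section 4.3 cover them regardless.

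**A profile is needed anyway.** Relating OS to the tumour profile does require one. That answers the second half of the objective, not the overall OS estimate or the blood-based work.

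**Conclusion.** The protocol gives incompatible definitions of who is followed for survival, and the narrower one does not deliver OS in the enrolled population named in section 2.2. That conclusion rests on the text alone.

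The consequence is conditional. If sections 3, 3.5 and 4.3 govern, OS is estimable only in a subset selected after enrolment, and the selection cannot be examined. A bias of known size or direction cannot be claimed: the protocol gives neither a failure rate nor a link to prognosis. In the illustration the overstatement of the median is under 0.1 month at 2% failures and at most about 1.5 months at 30% failures with a hazard ratio of 2. It is nil at a hazard ratio of 1, and would reverse if failures lived longer.

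This should be fixed, but it is not fatal. OS is a secondary objective of a portal protocol, and the primary objective does not depend on it.

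**What to change.** Reconcile sections 3, 3.5, 4.3 and 7 on one rule: every patient registered at Consent 2 with confirmed pancreatic cancer has vital status followed until death, whatever the tissue result or PRIMUS participation, unless consent to follow-up is withdrawn.

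In section 3.5, state that withdrawal for insufficient tissue does not end survival follow-up. Whether to attempt another biopsy is a clinical matter and need not be touched.

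Report OS for all registered patients alongside OS for profiled patients, with the number of tissue failures.

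The cost is a wording amendment and a small amount of passive data collection. Section 3.5 says Consent 2 already covers follow-up and data collection, and the NHS-record and annual eCRF routes are already in sections 4.3 and 7. The change is best made while patients are still being registered.

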#### **5 SAFETY REPORTING**

Study-related complications will be monitored on an on-going basis throughout the Study.

#### 5.1 **Definitions**

These definitions apply to all study participants from consent (Consent 1) to participate in the study.

Term	Definition
Adverse Event (AE)	An adverse event (AE) is any untoward medical occurrence
	in a subject to whom a medicinal product is administered,
	which does not necessarily have a causal relationship with
	this treatment/intervention.

Master Protocol; v2; 6th October 2017

# Related Adverse Event (RAE) A related adverse event (RAE) is any untoward and unintended occurrence in a subject administered trial treatment/intervention which is thought to be caused by or related to the trial treatment/intervention. **Serious Adverse Event (SAE)** A serious adverse event (SAE) means any untoward medical occurrence that at any dose requires the following, whether or not considered related to the trial treatment. Requires inpatient hospitalisation or prolongation of existing hospitalisation\* Results in persistent or significant disability or incapacity Results in a congenital anomaly/birth defect Is life-threatening (i.e. at the time of the event)\*\* Or results in death Is considered medically significant by the Investigator\*\*\* \*Requires in-patient hospitalisation should be defined as a hospital admission required for treatment of an AE. No time frame is specified for the duration of the admission. \*\*Life threatening means that the patient was at immediate risk of death from the event as it occurred. It does not include an event that, had it occurred in a more serious form, might have caused death. \*\*\*Considered medically significant by the Investigator are events that may not result in death, are not life threatening, or do not require hospitalisation, but may be considered a serious adverse experience when, based upon appropriate medical judgement, the event may jeopardise the patient and may require medical or surgical intervention to prevent one of the outcomes listed above. Medical and scientific judgement should be exercised in deciding whether an event is "serious" in accordance with this criterion. Serious and Related Adverse Event A serious and related adverse event (SRAE) is a SAE that (SRAE) may be related to trial treatment/intervention. The assessment of "relatedness" is primarily the responsibility of the Principal Investigator (PI) at site or agreed designee. SAEs will be considered related if the SAE is documented as possibly, probably or definitely related to protocol

Master Protocol; v2; 6th October 2017 IRAS: 184216

treatment. The assessment of relatedness is made using

	the following:	
	Relationship	Description
	Unrelated	There is no evidence of any causal relationship.
	Possible	There is some evidence to suggest a causal relationship (e, g. the event occurs within a reasonable time after administration of the trial treatment/intervention). However the influence of other factors may have contributed to the event (e.g. the patient's clinical condition, other concomitant treatments).
	Probable	There is evidence to suggest a causal relationship and the influence of other factors in unlikely.
	Definitely	There is clear evidence to suggest a causal relationship and other possible contributing factors can be ruled out.
Serious Related and Unexpected	A serious, related and unexpected Event (SRUE) is any	
Events (SRUE)	serious and related event, which is unexpected.	
	Unexpected is any event that is not listed in the protocol as	
	an expected event.	

N.B: To avoid confusion or misunderstanding of the difference between the terms "serious" and "severe", the following note of clarification is provided: "Severe" is often used to describe intensity of a specific event (for example CTCAE grade), which may be of relatively minor medical significance. "Seriousness" is the regulatory definition supplied above.

#### 5.2 Detecting, Recoding and Reporting of Adverse Events

Investigators must record all AEs in the patient notes whether they are required to be recorded in other trial documentation or not.

#### 5.2.1 Detection of Adverse Events

Participants will be asked at each trial visit about the occurrence of AEs since their last visit. AEs will be recorded, notified, assessed, reported, analysed and managed in accordance with the Health Research Authority (HRA) requirements.

AEs must be recorded as they are reported, whether spontaneously volunteered or in response to questioning about well being at trial visits. The questioning about AEs will cover the current visit as well as the period of time between the previous and the current visit.

Master Protocol; v2; 6th October 2017

